4.5.9.2 Approval by the Institutional Review Board or Ethics Committee

Collection and submission of biological samples to the RBR is contingent upon the review and approval of the exploratory research and the RBR portion of the Informed Consent Form by each site's Institutional Review Board or Ethics Committee (IRB/EC) and, if applicable, an appropriate regulatory body. If a site has not been granted approval for RBR sampling, this section of the protocol (Section 4.5.9) will not be applicable at that site.

4.5.9.3 Sample Collection

The following samples will be collected and stored in the RBR for research purposes, including, but not limited to, research on dynamic (non-inherited) biomarkers:

- Remaining blood derivatives (serum, plasma, PBMCs and their derivatives) after study-related tests have been performed
- Remaining FFPE tissue (with the exception of archival FFPE blocks, which will be returned to sites) after study-related tests have been performed
- Optional tissue samples collected for biopsy during the study

The following sample will be collected for research purposes, including, but not limited to, research on genetic (inherited) biomarkers

- Whole blood sample for DNA isolation

This sample will be collected from patients who have consented to optional RBR sampling at Cycle 1, Day 1 as shown in the schedule of assessments in [Appendix 1](#). If, however, the RBR genetic blood sample is not collected during the scheduled visit, it may be collected as soon as possible (after randomization) during the conduct of the clinical study. Collection of whole blood will enable the evaluation of single nucleotide polymorphisms in genes associated with immune biology including, but not restricted to, the target and pathway associated genes such as PD-L1, PD-1, and B7.1 as well as IL-8, IL-6, and related cytokines. The sample may be processed using techniques such as qPCR and DNA sequencing.

The above samples may be sent to one or more laboratories for DNA extraction to enable analysis of germline mutations, somatic mutations via whole genome sequencing (WGS), NGS, or other genomic analysis methods.

Genomics is increasingly informing researcher's understanding of disease pathobiology. WGS provides a comprehensive characterization of the genome and, along with clinical data collected in this study, may increase the opportunity for developing new therapeutic

approaches. Data will be analyzed in the context of this study but will also be explored in aggregate with data from other studies. The availability of a larger dataset will assist in identification of important pathways, guiding the development of new targeted agents.

For sampling procedures, storage conditions, and shipment instructions, see the Laboratory Manual.

RBR specimens are to be stored until they are no longer needed or until they are exhausted. However, the RBR storage period will be in accordance with the IRB/EC-approved Informed Consent Form and applicable laws (e.g., health authority requirements).

4.5.9.4 Confidentiality

Specimens and associated data will be labeled with a unique patient identification number.

Patient medical information associated with RBR specimens is confidential and may be disclosed to third parties only as permitted by the Informed Consent Form (or separate authorization for use and disclosure of personal health information) signed by the patient, unless permitted or required by law.

Given the complexity and exploratory nature of the analyses, data derived from RBR specimens will generally not be provided to study investigators or patients unless required by law. The aggregate results of any conducted research will be available in accordance with the effective Sponsor policy on study data publication.

Data generated from RBR specimens must be available for inspection upon request by representatives of national and local health authorities and Sponsor monitors, representatives, and collaborators, as appropriate.

Any inventions and resulting patents, improvements, and/or know-how originating from the use of the RBR data will become and remain the exclusive and unburdened property of the Sponsor, except where agreed otherwise.

4.5.9.5 Consent to Participate in the Research Biosample Repository

The Informed Consent Form will contain a separate section that addresses participation in the RBR. The investigator or authorized designee will explain to each patient the objectives, methods, and potential hazards of participation in the RBR. Patients will be told that they are free to refuse to participate and may withdraw their specimens at any time and for any reason during the storage period. A separate, specific signature will be required to document a patient's agreement to provide optional RBR specimens. Patients who decline to participate will not provide a separate signature.

The investigator should document whether or not the patient has given consent to participate and (if applicable) the date(s) of consent, by completing the RBR Research Sample Informed Consent eCRF.

In the event of an RBR participant's death or loss of competence, the participant's specimens and data will continue to be used as part of the RBR research.

4.5.9.6 Withdrawal from the Research Biosample Repository

Patients who give consent to provide RBR specimens have the right to withdraw their specimens from the RBR at any time for any reason. After withdrawal of consent, any remaining samples will be destroyed or will no longer be linked to the patient. If a patient wishes to withdraw consent to the testing of his or her specimens, the investigator must inform the Medical Monitor in writing of the patient's wishes through use of the appropriate RBR Subject Withdrawal Form and, if the study is ongoing, must enter the date of withdrawal on the RBR Research Sample Withdrawal of Informed Consent eCRF. The patient will be provided with instructions on how to withdraw consent after the study is closed. A patient's withdrawal from Study WO39210 does not, by itself, constitute withdrawal of specimens from the RBR. Likewise, a patient's withdrawal from the RBR does not constitute withdrawal from Study WO39210.

If a patient wishes to withdraw consent to the testing of his or her specimens after closure of the site, the investigator must inform the Sponsor by emailing the study number and patient number to the following email address:

[contact]

4.5.9.7 Monitoring and Oversight

RBR specimens will be tracked in a manner consistent with Good Clinical Practice by a quality-controlled, auditable, and appropriately validated laboratory information management system, to ensure compliance with data confidentiality as well as adherence to authorized use of specimens as specified in this protocol and in the Informed Consent Form. Sponsor monitors and auditors will have direct access to appropriate parts of records relating to patient participation in the RBR for the purposes of verifying the data provided to the Sponsor. The site will permit monitoring, audits, IRB/EC review, and health authority inspections by providing direct access to source data and documents related to the RBR samples.

4.5.10 Post-Treatment Assessments

Refer to Section 4.5.5 and [Appendix 1](#) for details of assessments of surveillance of RCC recurrence, including assessments following study treatment completion. After discontinuation of the study treatment, PRO questionnaires will be administered over the phone or at the site at end of treatment visit, the post-treatment visit, any visit for assessment of RCC recurrence, and at two timepoints after disease recurrence during survival follow-up. Post-study treatment follow-up visits for tumor recurrence

surveillance should also include monitoring for potential late serious adverse events and adverse events of special interest.

Following completion of the last treatment cycle, patients will return for a treatment discontinuation visit within 30 days of the last study dose and a post-treatment visit 3 months after the last dose.

Survival follow-up information will be collected via telephone calls, patient medical records, and/or clinic visits approximately every 3 months until death, loss to follow-up, consent withdrawal, or study termination by the Sponsor. All patients (irrespective of the arm to which they are randomized) will be followed for survival and new anti-cancer therapy information (including targeted therapies and immunotherapies) and subsequent progressions, unless the patient requests to be withdrawn from follow-up; this request must be documented in the source documents and signed by the investigator. If a patient withdraws from *the study*, study staff may use a public information source (e.g., county records) to obtain information about survival status.

4.6 PATIENT, TREATMENT, STUDY, AND SITE DISCONTINUATION

4.6.1 Patient Discontinuation

Patients have the right to voluntarily withdraw from the study at any time for any reason. In addition, the investigator has the right to withdraw a patient from the study at any time. Reasons for withdrawal from the study may include, but are not limited to, the following:

- Patient withdrawal of consent at any time
- Any medical condition that the investigator or Sponsor determines may jeopardize the patient's safety if he or she continues in the study
- Investigator or Sponsor determines it is in the best interest of the patient
- Patient non-compliance

Every effort should be made to obtain information on patients who withdraw from the study. Patients who withdraw their consent to be followed for the primary study endpoint (DFS) will be asked to continue follow-up for OS. The primary reason for withdrawal from the study should be documented on the appropriate eCRF. Patients who withdraw from the study will not be replaced.

4.6.2 Study Treatment Discontinuation

Patients must discontinue study treatment (atezolizumab/placebo) if they experience any of the following:

- Intolerable toxicity related to study treatment, including development of an immune-mediated adverse event determined by the investigator to be unacceptable given the individual patient's potential response to therapy and severity of the event
- Any medical condition that may jeopardize the patient's safety if he or she continues study treatment

- Use of another non-protocol anti-cancer therapy
- Pregnancy
- Disease recurrence (local recurrence, new primary RCC, or distant metastasis of RCC) documented by radiographic evidence, as determined by the IRF

The primary reason for study treatment discontinuation should be documented on the appropriate eCRF. Patients who discontinue study treatment prematurely will not be replaced.

4.6.3 Study and Site Discontinuation

The Sponsor has the right to terminate this study at any time. Reasons for terminating the study may include, but are not limited to, the following:

- The incidence or severity of adverse events in this or other studies indicates a potential health hazard to patients.
- Patient enrollment is unsatisfactory

The Sponsor will notify the investigator if the Sponsor decides to discontinue the study.

The Sponsor has the right to close a site at any time. Reasons for closing a site may include, but are not limited to, the following:

- Excessively slow recruitment
- Poor protocol adherence
- Inaccurate or incomplete data recording
- Non-compliance with the International Conference on Harmonisation (ICH) guideline for Good Clinical Practice
- No study activity (i.e., all patients have completed the study and all obligations have been fulfilled)

5. ASSESSMENT OF SAFETY

5.1 SAFETY PLAN

The safety plan for patients in this study is on the basis of clinical experience with atezolizumab in completed and ongoing studies. The anticipated important safety risks are outlined below (see Section 5.1.1).

Measures will be taken to ensure the safety of patients participating in this study, including the use of stringent inclusion and exclusion criteria and close monitoring of patients during the study. Administration of study drug (atezolizumab/placebo) will be performed in a monitored setting in which there is immediate access to trained personnel and adequate equipment and medicine to manage potentially serious reactions. After initiation of study treatment, serious adverse events and adverse events of special interest will continue to be reported until 90 days after the last dose of study treatment or

until initiation of new systemic anti-cancer therapy, whichever occurs first. All other adverse events will be reported until 30 days after the last dose of study treatment or until initiation of new systemic anti-cancer therapy, whichever occurs first. At each subsequent follow-up visit for tumor recurrence surveillance, monitoring for potential late-occurring adverse events should be performed. Guidelines for managing anticipated adverse events, including criteria for dosage modification and treatment interruption or discontinuation, are provided in Section 5.1.2 and in Appendix 11. Refer to Sections 5.2–5.6 for details on safety reporting during the study.

In the setting of a pandemic or epidemic, screening for active infections (including SARS-CoV-2) during study participation should be considered according to local or institutional guidelines or guidelines of applicable professional societies (e.g., American Society of Clinical Oncology or European Society for Medical Oncology).

Severe COVID-19 appears to be associated with a CRS involving the inflammatory cytokines IL-6, IL-10, IL-2, and IFN- γ (Merad and Martin 2020). If a patient develops suspected CRS during the study, a differential diagnosis should include COVID-19, which should be confirmed or refuted through assessment of exposure history, appropriate laboratory testing, and clinical or radiologic evaluations per investigator judgment. If a diagnosis of COVID-19 is confirmed, the disease should be managed as per local or institutional guidelines.

5.1.1 Risks Associated with Atezolizumab

Atezolizumab has been associated with risks such as the following: IRRs and immune-mediated hepatitis, pneumonitis, colitis, pancreatitis, diabetes mellitus, hypothyroidism, hyperthyroidism, adrenal insufficiency, hypophysitis, Guillain-Barré syndrome, myasthenic syndrome or myasthenia gravis, meningoencephalitis, myocarditis, nephritis, myositis, and severe cutaneous adverse reactions. Immune-mediated reactions may involve any organ system and may lead to hemophagocytic lymphohistiocytosis and macrophage activation syndrome (considered to be potential risks for atezolizumab). Refer to Appendix 11 of the protocol and Section 6 of the Atezolizumab Investigator's Brochure for a detailed description of anticipated safety risks for atezolizumab.

5.1.2 Management of Patients Who Experience Specific Adverse Events

There will be no dose modifications for atezolizumab/placebo in this study.

Study drug (atezolizumab or placebo) may be temporarily suspended in patients who experience toxicity considered to be related to study treatment. If study drug is withheld for >42 days from the last dose, the patient will be discontinued from study drug. If the investigator believes the patient is likely to derive clinical benefit and the Medical Monitor is in agreement, study drug can be resumed after being withheld for >42 days. If a patient must be tapered off steroids used to treat adverse events, the study drug may

be withheld for additional time beyond 42 days from the last dose until steroids are discontinued or reduced to prednisone dose (or dose equivalent) ≤ 10 mg/day. The investigator and the Medical Monitor will determine the acceptable length of treatment interruption.

Dose interruptions for reasons other than toxicity (e.g., surgical procedures) may be allowed *per investigator discretion*. The investigator *may consult* the Medical Monitor *to* determine the acceptable length of treatment interruption.

Guidelines for the management of patients who experience specific adverse events associated with atezolizumab are provided in [Appendix 11](#).

5.2 SAFETY PARAMETERS AND DEFINITIONS

Safety assessments will consist of monitoring and recording adverse events, including serious adverse events and adverse events of special interest, performing protocol-specified safety laboratory assessments, measuring protocol-specified vital signs, and conducting other protocol-specified tests that are deemed critical to the safety evaluation of the study.

Certain types of events require immediate reporting to the Sponsor, as outlined in Section [5.4](#).

5.2.1 Adverse Events

According to the ICH guideline for Good Clinical Practice, an adverse event is any untoward medical occurrence in a clinical investigation subject administered a pharmaceutical product, regardless of causal attribution. An adverse event can therefore be any of the following:

- Any unfavorable and unintended sign (including an abnormal laboratory finding), symptom, or disease temporally associated with the use of a medicinal product, whether or not considered related to the medicinal product
- Any new disease or exacerbation of an existing disease (a worsening in the character, frequency, or severity of a known condition), except as described in Section [5.3.5.10](#)
- Recurrence of an intermittent medical condition (e.g., headache) not present at baseline
- Any deterioration in a laboratory value or other clinical test (e.g., ECG, X-ray) that is associated with symptoms or leads to a change in study treatment or concomitant treatment or discontinuation from study treatment
- Adverse events that are related to a protocol-mandated intervention, including those that occur prior to assignment of study treatment (e.g., screening invasive procedures such as biopsies)
- Late complications related to surgery (e.g., urinary infection, intestinal obstruction, wound dehiscence, anastomotic leak or stricture)

5.2.2 Serious Adverse Events (Immediately Reportable to the Sponsor)

A serious adverse event is any adverse event that meets any of the following criteria:

- Is fatal (i.e., the adverse event actually causes or leads to death)
- Is life threatening (i.e., the adverse event, in the view of the investigator, places the patient at immediate risk of death)

This does not include any adverse event that had it occurred in a more severe form or was allowed to continue might have caused death.

- Requires or prolongs inpatient hospitalization (Section 5.3.5.11)
- Results in persistent or significant disability/incapacity (i.e., the adverse event results in substantial disruption of the patient's ability to conduct normal life functions)
- Is a congenital anomaly/birth defect in a neonate/infant born to a mother exposed to study treatment
- Is a significant medical event in the investigator's judgment (e.g., may jeopardize the patient or may require medical/surgical intervention to prevent one of the outcomes listed above)

The terms "severe" and "serious" are not synonymous. Severity refers to the intensity of an adverse event (e.g., rated as mild, moderate, or severe, or according to NCI CTCAE; see Section 5.3.3); the event itself may be of relatively minor medical significance (such as severe headache without any further findings).

Severity and seriousness need to be independently assessed for each adverse event recorded on the eCRF.

Serious adverse events are required to be reported by the investigator to the Sponsor immediately (i.e., no more than 24 hours after learning of the event; see Section 5.4.2 for reporting instructions).

5.2.3 Adverse Events of Special Interest (Immediately Reportable to the Sponsor)

Adverse events of special interest are required to be reported by the investigator to the Sponsor immediately (i.e., no more than 24 hours after learning of the event; see Section 5.4.2 for reporting instructions). Adverse events of special interest for this study include the following:

- Cases of potential drug-induced liver injury that include an elevated ALT or AST in combination with either an elevated bilirubin or clinical jaundice, as defined by Hy's Law (see Section 5.3.5.7)

- Suspected transmission of an infectious agent by the study treatment, as defined below

Any organism, virus, or infectious particle (e.g., prion protein transmitting transmissible spongiform encephalopathy), pathogenic or non-pathogenic, is considered an infectious agent. A transmission of an infectious agent may be suspected from clinical symptoms or laboratory findings that indicate an infection in a patient exposed to a medicinal product. This term applies only when a contamination of study treatment is suspected.

- Pneumonitis
- Colitis
- Endocrinopathies: Diabetes mellitus, pancreatitis, adrenal insufficiency, hyperthyroidism, and hypophysitis
- Hepatitis, including AST or ALT $>10 \times$ ULN
- Systemic lupus erythematosus
- Neurological disorders: Guillain–Barré syndrome, myasthenic syndrome, myasthenia gravis, and meningoencephalitis
- Events suggestive of hypersensitivity, IRRs, cytokine-release syndrome, influenza-like illness, HLH, and MAS
- Nephritis
- Ocular toxicities (e.g., uveitis, retinitis)
- Myositis
- Myopathies, including rhabdomyolysis
- Grade ≥ 2 cardiac disorders (e.g., atrial fibrillation, myocarditis, pericarditis)

5.3 METHODS AND TIMING FOR CAPTURING AND ASSESSING SAFETY PARAMETERS

The investigator is responsible for ensuring that all adverse events (see Section 5.2.1 for definition) are recorded on the Adverse Event eCRF and reported to the Sponsor in accordance with instructions provided in this section and in Sections 5.4–5.6.

For each adverse event recorded on the Adverse Event eCRF, the investigator will make an assessment of seriousness (see Section 5.2.2 for seriousness criteria), severity (see Section 5.3.3), and causality (see Section 5.3.4).

5.3.1 Adverse Event Reporting Period

Investigators will seek information on adverse events at each patient contact. All adverse events, whether reported by the patient or noted by study personnel, will be recorded in the patient’s medical record and on the Adverse Event eCRF.

After informed consent has been obtained **but prior to initiation of study treatment**, only serious adverse events caused by a protocol–mandated intervention (e.g., invasive

procedures such as biopsies, discontinuation of medications) should be reported (see Section 5.4.2 for instructions for reporting serious adverse events).

After initiation of study treatment, all adverse events will be reported until 30 days after the last dose of study treatment or until initiation of new systemic anti-cancer therapy, whichever occurs first, and serious adverse events and adverse events of special interest will continue to be reported until 90 days after the last dose of study treatment or until initiation of new systemic anti-cancer therapy, whichever occurs first.

Instructions for reporting adverse events that occur after the adverse event reporting period are provided in Section 5.6.

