4.5.6.2 Tumor Biopsy at the Time of Disease Recurrence

Biopsy at the time of first radiographic confirmation of disease recurrence is mandatory for all randomized patients. Biopsy can only be waived for patients who have no lesions amenable for biopsy at disease recurrence or if clinically infeasible, following discussion with the Medical Monitor.

Acceptable samples include resections; core needle biopsies for deep tumor tissue or lymph nodes; or excisional, incisional, punch, or forceps biopsies for cutaneous, subcutaneous, or mucosal lesions. For core needle biopsy specimens, at least three cores, embedded into a single paraffin block, should be submitted for evaluation.

The status of immune-related, tumor type-related, and other exploratory biomarkers (including, but not limited to, T-cell markers and tumor mutation status) in tumor tissue samples of enrolled patients may be evaluated.

Next-generation sequencing (NGS) may be performed by Foundation Medicine. If performed by Foundation Medicine, the investigator can obtain results from the samples

collected at the time of disease recurrence in the form of an NGS report, which is available upon request directly from Foundation Medicine. The investigator may share and discuss the results with the patient, unless the patient chooses otherwise. The Foundation Medicine NGS assay has not been cleared or approved by health authorities. The NGS report is generated for research purposes and is not provided for the purpose of guiding future treatment decisions.

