5.6 ADVERSE EVENTS THAT OCCUR AFTER THE ADVERSE EVENT REPORTING PERIOD

After the end of the adverse event reporting period (defined as 90 days for serious adverse events and adverse events of special interest and 30 days for all adverse

events after the last dose of study treatment), all deaths, regardless of cause, should be reported in the appropriate eCRF.

In addition, if the investigator becomes aware of a serious adverse event that is believed to be related to prior exposure to study treatment, the event should be reported through use of the Adverse Event eCRF if the eCRF is still available. Otherwise, the investigator should report these events directly to the Sponsor or its designee, either by faxing or by scanning and emailing the *Clinical Trial Adverse Event/Special Situations Form* using the fax number or email address provided to investigators.

5.7 EXPEDITED REPORTING TO HEALTH AUTHORITIES, INVESTIGATORS, INSTITUTIONAL REVIEW BOARDS, AND ETHICS COMMITTEES

The Sponsor will promptly evaluate all serious adverse events and adverse events of special interest against cumulative product experience to identify and expeditiously communicate possible new safety findings to investigators, IRBs, ECs, and applicable health authorities based on applicable legislation.

To determine reporting requirements for single adverse event cases, the Sponsor will assess the expectedness of these events using the following reference document:

- Atezolizumab Investigator's Brochure

The Sponsor will compare the severity of each event and the cumulative event frequency reported for the study with the severity and frequency reported in the applicable reference document.

Reporting requirements will also be based on the investigator's assessment of causality and seriousness, with allowance for upgrading by the Sponsor as needed.

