- ^{aa} After informed consent has been obtained but prior to randomization, only serious adverse events caused by a protocol-mandated intervention should be reported. Upon randomization into study, patients who experience a serious adverse event or protocol-defined adverse events of special interest will be followed for safety for 90 days following their last dose of study drug or until they receive another systemic anti-cancer therapy, whichever comes first. Patients who experience all other adverse events will be reported for patients until 30 days after the last dose of study, or until initiation of another systemic anti-cancer therapy, whichever occurs first. After this period, investigators should ensure any deaths, serious adverse events, or other adverse events of concern are reported if they are later assessed to be related to study treatment. Post-study treatment follow-up visits for tumor recurrence surveillance should include monitoring for potential late serious adverse events and adverse events of special interest. The investigator should follow each adverse event until the event has resolved to baseline grade or better, the event is assessed as stable by the investigator, the patient is lost to follow-up, or the patient withdraws consent. Every effort should be made to follow all serious adverse events considered to be related to study treatment or study-related procedures until a final outcome can be reported. Any medications given as treatment for an adverse event should be reported, even if given after the Treatment Discontinuation Visit.

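### A non-fatal serious complication of a mandated recurrence biopsy carries no explicit duty to report to the Sponsor once the 90-day safety window has closed

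*Protocol*

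**What the plan says.** - **The biopsy.** Protocol 4.5.6.2: "Biopsy at the time of first radiographic confirmation of disease recurrence is mandatory for all randomized patients". The exception is narrow: "Biopsy can only be waived for patients who have no lesions amenable for biopsy at disease recurrence or if clinically infeasible", after discussion with the Medical Monitor. Section 4.5.5 says the same, and 3.1.2 makes the requirement subject to the investigator's view of feasibility.
- **The definition.** Protocol 5.2.1 lists among adverse events: "Adverse events that are related to a protocol-mandated intervention, including those that occur prior to assignment of study treatment".
- **Before the first dose.** Sections 5.3.1 and 5.4.2.1 require reporting of SAEs caused by a protocol-mandated intervention. Section 5.3.1 gives biopsies as an example.
- **The window.** Section 5.3.1: "serious adverse events and adverse events of special interest will continue to be reported until 90 days after the last dose of study treatment". The same sentence adds an earlier stop: "or until initiation of new systemic anti-cancer therapy, whichever occurs first". Sections 5.1 and 5.4.2.2 and Appendix 1 footnote aa repeat the limit.
- **After the window.** Section 5.6 takes all deaths whatever the cause. Beyond that it asks for a report only "if the investigator becomes aware of a serious adverse event that is believed to be related to prior exposure to study treatment". Footnote aa says later events "are reported if they are later assessed to be related to study treatment".
- **Follow-up.** Section 5.5.1 asks for every effort to follow to a final outcome SAEs considered related to study treatment or to study-related procedures.

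**The concern.** The window is built around drug exposure, which lasts at most 16 cycles or 12 months. The mandated biopsy is triggered by recurrence, and surveillance for recurrence runs for years after the last dose. A pneumothorax or a bleed from a biopsy at Month 30 is an adverse event by the protocol's definition and may well be serious. It is not caused by study drug, so neither Section 5.6 nor footnote aa asks for it.

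The protocol already accepts that harm from its own procedures should be reported, but applies that rule only before treatment starts. Section 5.5.1 then expects procedure-related SAEs to be followed to outcome, which presupposes that they were recorded. At stake is whether the Sponsor and the data monitoring committee can judge the harm of an invasive procedure that serves partly for confirmation and partly for biomarker research.

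**Working it through.** **1. Which rule covers an SAE caused by a mandated biopsy?**

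| Time of biopsy | Explicit duty to report to the Sponsor? | Source |
|---|---|---|
| After consent, before first dose | Yes | 5.3.1, 5.4.2.1 |
| First dose to 90 days after last dose, before new systemic therapy | Yes, as any SAE | 5.3.1, 5.4.2.2 |
| Later, fatal | Yes, as a death | 5.6 |
| Later, not fatal | None found | 5.6, footnote aa |

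Three other passages might fill the last row, and none clearly does. Section 5.3.1 opens by asking for adverse events at every contact, but then sets the period and sends later events to 5.6. Section 5.4 asks for SAEs within 24 hours whatever their relationship to treatment, but points to 5.4.2, where the 90-day limit applies. Sections 4.5.10 and 5.1 and footnote aa ask for monitoring of late events at surveillance visits, without a duty to report those unrelated to study drug.

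**2. When does the window close?** (Cycle length from 3.1.1, maximum duration from Appendix 1; first dose taken as the day of randomization.)

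- Sixteen cycles without delay: last dose at 15 × 21 = 315 days; (315 + 90)/30.44 = 13.3 months.
- Last dose at 12 months: 12 + 90/30.44 = 15.0 months.

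It closes sooner for patients who stop early.

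**3. Reproducing the plan's figure** (Protocol 6.1.2, SAP 3.2: hazard ratio 0.70, two-sided 0.05, 90% power, 334 events).

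- Schoenfeld: 4(1.960 + 1.282)²/(ln 0.70)² gives 331.
- Freedman: (1.70/0.30)² × (1.960 + 1.282)² gives 338.
- Power with 334 events: 0.903.

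The planned 334 is reproduced.

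**4. Share of DFS events after the window.** Inputs from 6.1.2: exponential DFS with medians 47 and 67 months, 382 patients per arm, 33-month accrual with an 8-month ramp (taken as linear), and 5% loss per 24 months. For each arm, expected events by cutoff C are 382 × ∫ f(t) · 0.95^(t/24) · P(entry ≤ C − t) dt. Late events are the same integral over t beyond the closing time.

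| Cutoff | All events | After 13.3 months | After 15.0 months |
|---|---|---|---|
| Month 67 | 328.0 | 212.5 (65%) | 199.8 (61%) |
| Month 88 | 412.3 | 296.8 (72%) | 284.0 (69%) |

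The 328 at Month 67 is 1.8% below the plan's 334, so the model follows the design.

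**5. Sensitivity to early recurrence** (Weibull, control median 47 months, hazard ratio 0.70, Month 67).

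| Shape | Control 24-month DFS | Share after the window |
|---|---|---|
| 1.0 | 70.2% | 61-65% |
| 0.9 | 68.5% | 57-61% |
| 0.8 | 66.7% | 52-56% |
| 0.7 | 64.9% | 47-51% |
| 0.6 | 62.9% | 41-45% |

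The one placebo 24-month DFS rate quoted in Protocol 1.2.2.1, 68% in an adjuvant pembrolizumab trial, lies between shapes 0.8 and 0.9.

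**The case against.** A reader might infer that serious complications of most mandated biopsies are never reported, and that the Sponsor, the monitoring committee and the ethics committees cannot see them. The documents do not support that.

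- Fatal complications are captured, because 5.6 takes every death and SAP 5.6.2 summarizes deaths in follow-up.
- Sections 5.4 and 8.3 separately require investigators to meet local rules for reporting SAEs to health authorities and ethics committees.
- Surveillance visits include monitoring for late events. SAP 5.6.2 summarizes adverse events up to the clinical cutoff with no 90-day cap, so a late event that a site chooses to enter reaches the tables.
- The biopsy is not universal. It may be waived, Appendix 9 exempts brain lesions, and it lets solitary lung nodules be followed by imaging instead. Some procedures would also be done in ordinary care.
- The pre-treatment rule is not pointless, since 4.5.5 and Appendix 9 foresee biopsies during screening.
- Closure at new systemic therapy adds little, because biopsy comes at first radiographic confirmation and Appendix 2 asks for recurrence samples within two weeks.

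All of this stands and limits the point. It does not create a duty to report a non-fatal, non-drug-related SAE to the Sponsor after the window. The argument that a drug-based window is a legitimate design choice also has force, but it does not fit with 5.2.1, 5.5.1 and the protocol's own pre-treatment rule.

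**Conclusion.** The gap is real and comes from stated rules, not from silence. After the window, a non-fatal SAE caused by a mandated recurrence biopsy has no explicit route to the Sponsor.

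About 61-65% of projected DFS events by Month 67, and 69-72% by Month 88, fall in that period. This rests on the plan's exponential assumptions and on patients completing treatment. It counts DFS events, some of which are deaths without a biopsy. That most events fall late still holds for moderately front-loaded recurrence and fails by Month 67 at Weibull shapes of about 0.7 or lower. The gap itself does not depend on the share.

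The documents give no biopsy rate and no complication rate, so a count of missed events can only be illustrative: at an assumed 1-5% serious complication rate, each 100 late biopsies would bring 1 to 5 such events. Efficacy analyses, type I error and power are untouched.

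**What to change.** In Protocol 5.1, 5.3.1, 5.4.2.2 and 5.6 and Appendix 1 footnote aa, extend the existing pre-treatment rule. SAEs caused by a protocol-mandated intervention, including the recurrence biopsy, should be reported to the Sponsor at any time during study participation, regardless of time since the last dose or the start of new therapy. All five places need the change, because leaving one as it stands would create a new contradiction.

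In SAP 5.6.2, add a summary of these events separate from other adverse events. Section 5.3.4 asks only about relation to study treatment, so sites would need a way to mark an event as procedure-related on the adverse event form.

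The cost is a short amendment, that marking on the form, one added summary and a small number of extra SAE reports.
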